**Table 3-1 Objectives and related endpoints**

Objective	Endpoint	Analysis
Primary		

 
To evaluate both formulations on patient compliance, using stick pack/tablet count over 24 weeks of treatment in ICT naïve patients during core phase
 
To evaluate the change from baseline in serum ferritin after 24 weeks of treatment for both formulations in ICT naïve patients during the core phase
 
	
 
Compliance measured by stick pack/tablet count over 24 weeks of treatment (i.e. assessed at week 25 visit)
 
Change from baseline in serum ferritin after 24 weeks of treatment (i.e. serum ferritin at week 25 visit)
 
	Refer to Section 10.4 Refer to Section 10.4
Secondary (Core phase)		
To evaluate both formulations on change in serum ferritin and compliance in ICT naïve patients, after 48 weeks of treatment	
 
Compliance measured by stick pack/tablet count after 48 weeks of treatment
 
Change from baseline in serum ferritin after 48 weeks of treatment
 
	Refer to Section 10.5.1
To evaluate both formulations on change in serum ferritin after 24 weeks and 48 weeks of treatment in ICT naïve and pre-treated patients	Change from baseline in serum ferritin after 24 weeks (i.e. assessed at week 25 visit) and 48 weeks of treatment	Refer to Section 10.5.2
To evaluate both formulations on patient satisfaction and palatability using Patient / Observer Reported Outcomes (PRO/ObsRO) questionnaires	Domain scores of treatment satisfaction and palatability over time	Refer to Section 10.5.3
To evaluate both formulations on overall safety	Overall safety, as measured by frequency and severity of adverse events (including active monitoring for renal toxicity; including renal failure, hepatic toxicity; including hepatic failure, and gastrointestinal hemorrhage), and changes in laboratory values from baseline (serum creatinine, creatinine clearance, ALT, AST, RBC and WBC). In addition, vital signs, physical, ophthalmological, audiometric, cardiac, and growth and development evaluations will be assessed.	Refer to Section 10.5.4
To evaluate compliance using a daily PRO/ObsRO questionnaire	Rate of dosing instructions deviations (doses missed / not taken at the same time every day)	Refer to Section 10.5.5

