Medication labels will comply with the legal requirements of the countries where the study is implemented and be printed in the local language. They will supply no information about the patient. Only the patient identifier will be entered on the medication label by the investigator or pharmacist before the corresponding medication is handed out to the patient. The storage conditions for study drug will be described on the medication label.

Patients randomized to Treatment arm 1 will take the deferasirox DT every day on an empty stomach, at least 30 minutes before the next meal. The patient will disperse the required number of deferasirox tablets in an appropriate amount of water, apple juice or orange juice. Gentle stirring should be applied and continued until the tablets are fully disintegrated, which takes approximately 1 to 3 minutes. Immediately, after full disintegration of the tablets, the entire content of the glass should be swallowed.

Patients randomized to Treatment arm 2 should administer the granules by sprinkling the full dose on a soft food (e.g., yogurt, applesauce or warm porridge). The dose should be immediately and completely consumed, and not stored for future use. The granules should be taken once a day, preferably at the same time each day, and may be taken on an empty stomach or with a light meal.

It is recommended that the doses be timed such that they occur at almost the same time each day. For example, if the patient took the study medication at 8:00AM on first day of treatment, the subsequent dose would also be taken at approximately 8:00AM on the next day, and so on.

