## **7 Visit schedule and assessments**

### **7.1 Study flow and visit schedule**

[Table 7-1](#) lists all of the assessments for the core phase and [Table 7-2](#) lists all of the assessments for the optional extension phase and both indicate with an "X", the visits when they are performed. Patients in the core phase who complete Visit 16 and decide to proceed to the optional extension phase will begin following all the assessments included in the visit 777 in [Table 7-1](#) and then follow the optional extension assessment visit 17 listed in [Table 7-2](#) on the

same day so as to avoid a gap in treatment. Patients who were on the DT arm during core phase of study who have switched to granules at Visit 17 as part of the optional extension phase will need to return weekly (Visits 18, 19 and 20) for the first month after beginning the optional extension phase (granules) for serum creatinine and creatinine clearance. Thereafter they will follow the same schedule as patients who were on granules arm during the core phase. Visit 778 should not be completed by patients who continue into the optional extension phase. Should a patient discontinue the core phase at or prior to Visit 16, they should perform Visits 777 and 778 including safety follow up as per [Table 7-1](#).

Patients in the optional extension phase will complete Visit 779 and 780 at the end of the study or in case of earlier discontinuation.

Patients should be seen for all visits to perform the scheduled assessments on the designated day, or as close to is as possible, i.e., for the core phase not exceeding  $\pm$  2 days for assessments scheduled in Visits 1 to 6 and  $\pm$  7 days for all other visits until End of Treatment Visit 777. For the optional extension phase, not exceeding  $\pm$  7 days for all visits until End of Treatment Visit 779. In this clinical trial, a week is 7 calendar days. For yearly assessments in extension phase, i.e. audiology, ocular and growth and development examinations,  $\pm$  30day window is allowed.

All visits should be scheduled respective to the randomization date (Visit 3) for the core phase, rather than in relation to the previous visits. For the optional extension phase, all visits should be scheduled respective to Visit 17.

All data obtained from these assessments must be supported in the patient's source documentation. No eCRF pages will be used as a source document.

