The palatability questionnaire will be completed at Visits 4 (Week 2), 5 (Week 3), 11 (Week 25), and 777 (day of the last dose of treatment), in order to co-administer this questionnaire together with the modified SICT questionnaires. The Visit 4 palatability assessment will be considered as baseline and the Visit 5 assessment will allow to check the test-retest reliability within trial.

The handheld devices will be enabled with alarms that will remind the patient / caregiver to complete the modified SICT and the palatability questionnaires at the time points specified above.

The compliance questionnaire will be completed daily, starting at Visit 3 until Visit 777 (day of the last dose of treatment). This questionnaire asks whether the study medication was taken by the patient / given by the caregiver and at what time it was ingested. Alarms and reminders will prompt patients to complete the compliance questionnaire every day.

Daily diary records will be used to calculate the rate of dosing instructions deviations in each study arm (doses missed completely or not taken at approximately the same time every day).

PRO/ObsRO questionnaires as well as the compliance diary will not be collected during optional extension phase.

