#### 7.2.5.1 PK blood sample collection and handling

##### 7.2.5.1.1 Blood collection plan

PK blood samples will be collected in all patients **[Egypt: no PK samples will be collected]** at weeks 1, 3, 5, 9, 13, 17, 21, 25, 29, 33, 37, 41 and 45 visits to support the assessment of compliance (see [Table 7-5](#)). Patients / caregivers will be instructed that study drug should not be administered in the morning of these visits.

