### 10.5.5 To evaluate compliance using a daily PRO/ObsRO questionnaire

Patient adherence to medication regimen instructions will be assessed via daily diary records (PRO / ObsRO questionnaire) providing information on two dimensions: whether the study medication is consumed and the time of medication intake. These data will be summarized over time by descriptive statistics for both formulations. The rate of dosing instructions deviations (doses missed completely or not taken at approximately the same time every day) will be calculated for each study arm.

The FAS-1, FAS-2 and FAS-3 will separately be used for the analysis of compliance using a daily PRO/ObsRO questionnaire.

Details about scoring and analyses will be included in the SAP.

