### **2.9.1.3 Compliance diary**

The Compliance questionnaire consists of 2 items. Item 1 assessed whether the medication was taken (yes/no) and Item 2 is a record of the time when the medication was taken with a not applicable option for patients who did not take their ICT.

The daily compliance questionnaire diary records will also be used to calculate the rate of dose violations. For a given day, a dose violation is defined as a dose that is either missed completely or not taken in accordance with the timing instruction (no later than 12:00 pm). The dose violation rate is calculated as:

$$[\text{Number of dose violations} / \text{Drug exposure (days)}] * 100$$

Weekly average of dose violation rate will be calculated and summarized using descriptive statistics by treatment arm, type of questionnaire (ObsRO questionnaire versus PRO questionnaire) and week (weeks 1, 13, 25, 37 and core EOT). Additionally, absolute change from week 1 will be tabulated including 95% confidence intervals for mean. A graphical representation will be provided over all week periods by treatment arm and type of questionnaire. The y-axis will be the mean and SD and the x-axis will be the corresponding week period (see [Table 4-3](#) for week periods definition).

Due to the use of ePRO there will be no individual items missing. The weekly average rates will be calculated when there are at least four non missing daily responses. For a given week the denominator will be the number of non-missing days. No additional imputation will be carried out.

The number of patients completing the compliance diary and the number of expected and missing days will be summarized by each treatment arm and type of questionnaire for the FAS-3.

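### The two SAPs that score the diary judge dose timing against an undeclared 12:00 pm limit, whereas the named endpoint is consistency of dosing time from day to day

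*SAP*

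**What the plan says.** **Endpoint.** Protocol Table 3-1 gives "Rate of dosing instructions deviations (doses missed / not taken at the same time every day". Table 1-1 of SAP Amendment 3 and of the End of Core Phase SAP carries the same entry. Protocol 7.2.3 and 10.5.5 describe the rate as covering "doses missed completely or not taken at approximately the same time every day". Section 10.5.5 adds that the diary informs on "two dimensions: whether the study medication is consumed and the time of medication intake", and leaves scoring details to the SAP.

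**Instruction to patients.** Protocol 6.1.1: "It is recommended that the doses be timed such that they occur at almost the same time each day". It mentions 8:00 AM only as an example.

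**Scoring rule.** SAP Amendment 3 section 2.9.1.3 and End of Core Phase SAP section 2.9.5.3 count a dose as a violation if it is missed or "not taken in accordance with the timing instruction (no later than 12:00 pm".

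**Declared changes.** The changes table in section 3 of SAP Amendment 3 reads NA. The one in the End of Core Phase SAP lists average daily dose, concomitant medication and vital-sign thresholds, with nothing on the diary.

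**PK visits.** Protocol 7.2.5.1.1: "Patients / caregivers will be instructed that study drug should not be administered in the morning of these visits". The listed visits include weeks 1, 13, 25 and 37. No PK samples are taken in Egypt.

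**The concern.** Consistency of dosing time and lateness against a fixed clock time are different quantities. If 12:00 pm means noon, a family that doses regularly in the evening is scored like one that misses every dose, while erratic dosing before noon goes unseen. If midnight was meant, the timing part does nothing on the dosing day. Each SAP therefore contradicts its own objectives table.

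The result is a single rate that readers would take for the protocol's measure of dosing-instruction deviations but which is not that measure. It also cannot show whether missed doses or clock time drives it, although protocol 10.5.5 names these as two dimensions.

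The noon reading also sits awkwardly with the instruction not to dose in the morning of PK visits. The tabulated weeks 1, 13, 25 and 37 nominally begin on such a day, and week 1 is the reference for change.

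**Working it through.** There is no figure in the plan to reproduce, so the check compares the two definitions and then scores example diaries under each.

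**1. Definitions side by side**

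| Place | A deviation is |
|---|---|
| Protocol Table 3-1, 7.2.3, 10.5.5 | missed, or not at (about) a constant daily time |
| Table 1-1, SAP Amendment 3 and End of Core Phase SAP | the same as the protocol |
| SAP Amendment 3 2.9.1.3; End of Core Phase SAP 2.9.5.3 | missed, or later than 12:00 pm |

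**2. Example weeks.** All seven doses are taken and seven diary days are completed. Weekly rate = violations / non-missing diary days × 100, the weekly denominator in 2.9.1.3. The noon rule flags any dose after 12:00. The own-median rule flags any dose further from that week's median time than the tolerance. The documents give no tolerance, so 1, 2 and 3 hours are assumed; the results are the same for all three.

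| Pattern | Noon rule | Own-median rule | 12:00 pm read as midnight |
|---|---|---|---|
| 18:00 on 7 days | 7/7 = 100% | 0/7 = 0% | 0% |
| 11:30 on 4 days, 12:30 on 3 | 3/7 = 42.9% | 0/7 = 0% | 0% |
| 05:00 on 4 days, 11:45 on 3 | 0/7 = 0% | 3/7 = 42.9% | 0% |

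In the second row the median is 11:30, and 12:30 is exactly 60 minutes away, so it is not outside a 1-hour tolerance. In the third row the median is 05:00, and 11:45 is 6 h 45 min away.

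**3. PK-visit days.** SAP Table 4-3 sets diary week y as days (y−1)×7+1 to y×7:

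- week 1: days 1–7
- week 13: days 85–91
- week 25: days 169–175
- week 37: days 253–259

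The nominal PK visits fall on days 1, 85, 169 and 253, the first day of each tabulated week. If that day's dose is taken after noon:

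- with seven diary days, the weekly rate rises by 1/7 = 14.3 points;
- at the minimum the SAP accepts ("The weekly average rates will be calculated when there are at least four non missing daily responses"), it rises by up to 1/4 = 25.0 points.

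The visit need not fall in that diary week. The protocol 7.1 window is plus or minus "7 days for all other visits until End of Treatment Visit 777", so at weeks 13, 25 and 37 there are 15 possible visit days (−7 to +7), of which 7 (0 to +6) lie in the tabulated week. This assumes that treatment starts on the randomization day.

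**The case against.** The strongest reply is delegation. The protocol gives no tolerance or reference time and hands scoring details to the SAP, so a sponsor could regard the clock limit as such a detail and NA in the changes table as honest. The limit may also come from diary or training material outside these documents; I did not have the body of Table 7-1 either. It is fair that the source is unseen rather than proved absent. But delegated detail could set a tolerance or a reference time. It does not extend to replacing consistency with lateness, and a limit found in a manual would still not match the endpoint in the SAPs' own Table 1-1.

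Four further points stand in part:

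- The protocol itself specifies one combined rate, so separate reporting is an improvement suggested by the two-dimensions wording, not the repair of a SAP departure.
- PK days do not separate the rules. A usual 08:00 doser delayed to 13:00 is flagged by both. A morning blood draw followed by a dose before noon is also possible, so how often the PK effect occurs is unknown.
- The examples are chosen patterns. With six diary days split 05:00 ×3 and 11:45 ×3, the median is 08:22:30 and every dose is 3 h 22.5 min away: 100% at 1 to 3 hours, 0% at 4 hours. A one-week median is unstable.
- The endpoint is descriptive, is one of several adherence measures, and is not repeated in the final SAP.

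These limit the impact. They do not make the scored quantity the named one.

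**Conclusion.** The concern holds. Followed as written, the two SAPs do not measure the secondary endpoint they name, whether 12:00 pm means noon or midnight, and the departure is not declared. For individual patients, the noon rule and a consistency rule can differ by as much as 100 percentage points (18:00 daily), and the disagreement can run in either direction. These are illustrations under assumed tolerances of 1 to 3 hours, not estimates for the trial.

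The effect on the comparison of arms is of unknown size and direction; the PK schedule is the same in both. The PK-day effect arises only if that day's dose falls after noon and the visit falls within the diary week. There is no hypothesis test on this endpoint, and the co-primary analyses do not use it. Other adherence measures remain: pill count, the modified SICT adherence items and pre-dose PK. The point should be corrected, but it does not threaten the main conclusions.

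**What to change.** - Score timing against the protocol endpoint: a deviation is a dose outside a pre-stated tolerance around the patient's own usual diary time, for example a median. State the period over which that median is taken, since a single week can be unstable.
- Report missed doses and timing deviations separately, with the combined rate alongside if wanted.
- State how PK-visit days are handled, including day 1 in the week-1 reference.
- The sponsor should say whether noon was meant and reconcile the 12:00 pm statement with the protocol's dosing and PK-visit text.
- If the rate already reported is kept, label it as missed or post-noon doses (if noon was meant) and list it as a change from the protocol.

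The cost is SAP wording plus a small supplementary analysis. Daily intake and clock times are already recorded, so no new data are needed. Because the final SAP does not plan to repeat this endpoint, the rescoring or relabelling would be an addendum to the End of Core Phase results.

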### **2.9.2 Safety evaluations**

Unless otherwise specified, the following analyses will be performed separately for the Safety Set 1, Safety Set 2, Safety Set 3 for the core phase and the Safety Set-4 for the entire granule period. Listings will be provided for the Safety Set 3 and the Safety Set-4.

#### **On-treatment period**

For the core phase, the overall observation period will be divided into three mutually exclusive segments taking into account stop rules as per [Table 2-1](#):

- Pre-treatment period: from day of patient's first informed consent to the day before first dose of study drug;
- On-treatment period: from day of first dose of study drug to 30 days after last dose of study drug;
- Post-treatment period: starting at day 30+1 after last dose of study treatment.

For the entire granule period, the following conventions will be taken into account while deriving the three observation periods:

- For patients enrolled in DT formulation in the core phase, the pre-treatment period will not be derived;
- For patients enrolled in Granule formulation in the core phase, the first dose of study drug will be the day of first dose in the core phase.

Unless otherwise specified, the safety summary tables will include only assessments from the on-treatment period.

All data, regardless of observation period, will be listed. Safety assessments starting during the pre-treatment or post-treatment period will be flagged in the listings. Safety assessments starting prior to study day 1 will appear with negative study day in the listings.

### **Adverse events**

AEs will be coded using the latest version of Medical Dictionary for Regulatory Activities (MedDRA) available prior to clinical database lock.

Any information collected (e.g. relatedness to study drug, action taken etc.) will be listed.

The following adverse event summaries will be produced by treatment arm:

- Adverse events (overall and severe), regardless of study drug relationship by primary system organ class and preferred term
- Adverse events, regardless of study drug relationship by primary system organ class and preferred term and severity
- Adverse events (overall and severe), with suspected study drug relationship by primary system organ class and by preferred term
- Serious adverse events (overall and severe), regardless of study drug relationship, by primary system organ class and preferred term
- Serious adverse events (overall and severe), with suspected study drug relationship, by primary system organ class and preferred term
- Adverse events leading to study drug discontinuation (overall and severe), regardless of study drug relationship, by primary system organ class and preferred term
- Adverse events requiring dose adjustment or study-drug interruption (overall and severe), regardless of study drug relationship, by primary system organ class and preferred term
- Adverse events requiring additional therapy (overall and severe), regardless of study drug relationship, by primary system organ class and preferred term
- Deaths (all and on-treatment) by primary system organ class and preferred term (Safety Set 3 and 4 only).

For the legal requirements of ClinicalTrials.gov and EudraCT, two required tables will be produced for the Safety Set 3 on combined core and extension phases at the time of the final CSR:

- Non-serious adverse events with an incidence greater than 5%;

- Serious adverse events (SAE) and SAE suspected to be related to study treatment will be provided by system organ class and preferred term. The number of deaths resulting from SAEs suspected to be related to study treatment and SAEs irrespective will also be provided.

If for a same patient, several consecutive AEs (irrespective of study treatment causality, seriousness and severity) occurred with the same SOC and PT:

- a single occurrence will be counted if there is  $\leq 1$  day gap between the end date of the preceding AE and the start date of the consecutive AE
- more than one occurrence will be counted if there is  $> 1$  day gap between the end date of the preceding AE and the start date of the consecutive AE

For occurrence, the presence of at least one SAE / SAE suspected to be related to study treatment / non SAE has to be checked in a block e.g., among AE's in a  $\leq 1$  day gap block, if at least one SAE is occurring, then one occurrence is calculated for that SAE.

AEs will be summarized by presenting the number and percentage of patients having at least one AE, and having at least one AE by system organ class and/or preferred, severity and relation to study drug by treatment arm. A patient with multiple occurrences of an AE will be counted only once in the AE category.

An overall summary of type of AEs (e.g. serious, leading to study drug discontinuation, requiring dose adjustment or/and interruption) will be presented by severity and treatment arm.

All AEs will be listed. Any information collected (e.g. regardless to study drug, action taken etc.) will be listed as well as the duration of the AE. The listings of all deaths, serious adverse events, adverse events leading to study drug discontinuation, and adverse events requiring dose adjustment or interruption will also be provided.

